2.4 Exclusion criteria

Exclusion criteria are as follows: (a) serious pregnancy complications such as placenta previa, placenta accreta spectrum, eclampsia, and grade 3 or higher cardiac issues per NYHA standards; (b) challenges in initiating mother-infant SSC include emergencies such as neonatal asphyxia or respiratory distress, maternal excessive bleeding during surgery, and maternal infectious dermatoses; (c) previous breast

IMMEDIATE SKIN-TO-SKIN CONTACT DURING CAESAREAN SECTION

1 surgeries such as biopsies or augmentations, nipple inversions complicating
2 breastfeeding, or taking medications affecting lactation.

3 **2.5 Randomization and Blinding**

4 A randomization sequence will be generated using Microsoft Excel 2010 with
5 block randomization in blocks of four via a central system. Random distribution cards
6 will be placed in numbered opaque envelopes, each corresponding to a card. As
7 eligible participants enrolled, envelopes will be opened sequentially to assign
8 treatments based on predetermined groupings. The randomization plan will be
9 designed by a public health graduate student specializing in medical statistics, who
10 will not be involved in the clinical phase. Staff performing SSC during and after
11 cesarean will be blinded to the randomization procedure, and data collectors and
12 statistical analysts will be unaware of patient groupings. However, blinding of patients
13 will not be feasible.

14 **2.6 Experimental Group (EG)**

15 2.6.1 Administration of SSC and BF during CS

16 A multidisciplinary team, including obstetricians, pediatricians, anesthetists,
17 nursing staff, and other personnel, collaborates to implement a SSC and BF during CS
18 (skin-to-skin contact and breastfeeding during cesarean section) protocol for the
19 intervention. Following spinal anesthesia, the gynecologist initiates surgery with double
20 sterile gloves and arm sleeves. The pediatrician remains on standby in the adjacent
21 neonatal resuscitation room to manage any distress in the newborn. As the neonate is
22 delivered, the surgical drape is lowered, allowing the parents to witness the birth. The
23 neonate, facing the parents, is gently placed on the mother's chest by an obstetric nurse.
24 Before resuming the procedure, the surgeon removes one pair of gloves and sleeves,
25 and the sterile barrier is reestablished. If the neonate exhibits no signs of distress, it

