1 2.8.1 Primary outcome

2 (A) Incidence of neonatal hypoglycemia: Neonatal blood glucose levels will be
3 assessed using the Stat Strip Xpress glucose meter at 1, 3, and 6 hours after birth.
4 Hypoglycemia is categorized as follows: mild hypoglycemia (overall) at <45 mg/dL,
5 moderate-to-severe at <36 mg/dL, and severe at <18 mg/dL. Treatment will be
6 initiated if levels dropped below 25 mg/dL or if symptoms like shakiness, tachycardia,
7 pallor, hypothermia, hunger, sweating, or weakness appeared⁸. In such cases, 10
8 ml/kg of formula will be administered, followed by a recheck after 0.5 hour. If levels
9 rise above 40 mg/dL, subsequent checks occurs every 3 hours⁹. Persistent levels
10 below 50 mg/dL necessitates continued formula feeding and monitoring, or
11 transferred to neonatal care if needed.

12 2.8.2 Secondary outcome

13 (A) Breastfeeding initiation and duration of first breastfeeding, characterized by
14 newborns correctly latching onto the nipple and areola, and establishing regular,
15 effective sucking and swallowing, will be immediately assessed post-operation, with
16 timing recorded to the minute.

17 (B) Onset of lactogenesis II, approximately 72 hours post-delivery, marked by
18 significant milk secretion perceived by the mother as breast fullness, confirmed by
19 observing and squeezing the areola to assess milk spillage, will be assessed from
20 delivery to pre-discharge, with timing recorded to the hour postpartum.

21 (C) Exclusive breastfeeding rate during hospitalization, where newborns are
22 exclusively breastfed except for vitamins and minerals. This rate will be calculated for
23 mothers who underwent cesarean delivery in both study groups.

24 **2.9 Data Collection and Management**

25 Researchers will contact all women scheduled for cesarean deliveries within 24
26 hours before the procedure. Led by the principal investigator and an experienced
27 research assistant, the team will conduct face-to-face interviews to gather
28 demographic and obstetric information. Details regarding the duration of SSC, the
29 initiation and duration of the first breastfeeding session, exclusive breastfeeding

IMMEDIATE SKIN-TO-SKIN CONTACT DURING CAESAREAN SECTION

1 during hospitalization, as well as the infant's safety and blood glucose levels, will be
2 continuously collected and recorded by trained staff during and after elective cesarean
3 sections. All data will be anonymized and de-identified for further evaluation.

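### Section 2.5 says data collectors do not know the arm; section 2.9 makes this wrong for skin-to-skin duration and first feed, and unsupported for the other outcomes

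*Protocol*

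**What the plan says.** Protocol section 2.5 covers three groups of personnel in one sentence. Staff who perform SSC during and after the "cesarean will be blinded to the randomization procedure, and data collectors and" then "statistical analysts will be unaware of patient groupings". So data collectors and analysts are both said not to know the allocation, and no outcome is excepted. The next sentence names only patients as a group that cannot be blinded.

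Section 2.9 describes the collection of outcome data. The items are SSC duration, "initiation and duration of the first breastfeeding session, exclusive breastfeeding" (the last of these over the hospital stay), infant safety and blood glucose. They are to be "continuously collected and recorded by trained staff during and after elective cesarean" section. No second, separately blinded team is named for any of them.

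Section 2.8.1 has glucose "assessed using the Stat Strip Xpress glucose meter at 1, 3, and 6 hours after birth". Section 2.8.2 defines first-feed initiation and duration by correct latch and effective sucking, timed to the minute. Lactogenesis II is "significant milk secretion perceived by the mother as breast fullness, confirmed by" inspection and squeezing of the areola. Exclusive breastfeeding is counted during the hospital stay.

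**The concern.** What separates the arms is SSC and breastfeeding in theatre against SSC after surgery. A person who times SSC or a first feed in theatre is therefore watching the allocation itself. A protocol that calls this person blinded claims a property that its design cannot have for those items.

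What is at stake is the account of detection bias. Whether a latch is correct, or sucking effective, is a judgement. If section 2.5 is carried into the report as it stands, readers will take such judgements as blinded when they were not.

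A second, smaller route concerns glucose. Under 2.8.1, symptoms as well as low values can prompt formula and a recheck. Some of the listed signs are matters of observation, and the staff who notice them may know the arm. The section does not say whether a prompted recheck counts towards incidence. If it does, knowledge of the arm could influence how many readings an infant contributes. Formula given on symptoms would also end exclusive breastfeeding as 2.8.2 defines it.

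**Working it through.** No arithmetic applies, because the claim depends on no rate, effect size or sample size. The check sets sections 2.5 to 2.9 side by side.

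1. **Scope of the claim.** Section 2.5 speaks of data collectors without qualification. To be true, it must hold for everyone who records an outcome.
2. **Who records, and when.** Section 2.9 gives trained staff, recording continuously, during and after the operation. SSC duration and the first feed are on the list.
3. **What is visible at that time.** In 2.6.2 the experimental infant is placed on the mother's chest at birth, SSC lasts through the operation, and the nurse helps start feeding early. In 2.7.1 the control infant is dried, the cord is clamped, and the infant goes to the ward until surgery ends.
4. **Consequence for SSC duration.** Any SSC clocked during surgery belongs to the experimental arm. The recorder cannot fill in the item without learning the arm.
5. **Consequence for the first feed.** A control infant following 2.7.1 cannot feed from the mother during surgery, so a feed timed then identifies the arm. Section 2.8.2 places the assessment immediately after the operation, but 2.9 includes the first feed among items recorded during it, and a feed that starts in theatre has to be observed there to be timed to the minute.
6. **Later outcomes.** Glucose is read at 1, 3 and 6 hours after birth. Control SSC starts within one hour of birth, so at 3 and 6 hours the arms need not look different. Lactogenesis II is expected at about 72 hours, and exclusive breastfeeding is recorded over the stay. A ward assessor who was not in theatre could be unaware of the arm; the protocol neither names such a person nor says that the theatre staff take these readings.

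| Item | When recorded | Status of the blinding claim |
|---|---|---|
| SSC duration | In theatre and after | Contradicted |
| First-feed initiation and duration | In theatre and after | Contradicted |
| Glucose (primary) | 1, 3 and 6 hours after birth | Unsupported, not disproved |
| Lactogenesis II | Delivery to discharge, about 72 hours | Unsupported, not disproved |
| Exclusive breastfeeding | Hospital stay | Unsupported, not disproved |
| Analysis | Not applicable | Not contradicted |

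**The case against.** The strongest defence is that section 2.9 does not say one set of people records everything, and that the primary outcome is a meter value set against a numeric cut-off, read after theatre. Hypoglycemia is classified by glucose level; symptoms start treatment but do not define the outcome. The protocol also already states that mothers are not blinded, and lactogenesis II does not rest on the mother's perception alone. All of this stands. It confines the proven contradiction to the items observed in theatre, but it does not rescue a sentence that exempts none of them.

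Three stronger readings are tempting, and the documents do not support them:

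- A reader might infer that no outcome has blinded assessment, the primary included. The text leaves room for a separate ward assessor, so for glucose the right word is unsupported.
- A reader might infer that the protocol claims SSC staff are blind to the arm. It says they are blind to the randomization procedure, which can mean only that they do not know how the sequence is made. The same sentence uses different words for data collectors.
- A reader might infer that a couple of reclassified readings would overturn the primary result. Nothing in the protocol indicates that readings would be reclassified. The section 2.10 control rate gives 5.3% × 148 = 7.8, about 8 events against 0. Removing two leaves 6 against 0, with Fisher P = 0.030 at 148 per arm, still below 0.05. Two events added to the experimental arm would matter (8 against 2, P = 0.10), but the documents give no reason to expect them.

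**Conclusion.** The point holds in a limited form. The blanket statement in section 2.5 is wrong for SSC duration and for first-feed initiation and duration, which form one of the three secondary outcomes. It is unsupported for the primary outcome and for the other two secondary outcomes. The statement on analysts is not in question.

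This rests on two readings: that the trained staff of section 2.9 are among the data collectors of section 2.5, and that recording during the caesarean means being present or otherwise aware of what happens in theatre. If data collectors meant only the team that interviews women before surgery, the contradiction would go, but section 2.5 would then make no claim about outcome assessment and should say so.

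No numerical size can be given, and nothing shows that the primary result is compromised. The consequence is for what the report may claim about detection bias. The point should be corrected because a false statement of blinding is easy to remove now and hard to defend later.

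**What to change.** In section 2.5, withdraw the unrestricted claim about data collectors and state instead:

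- Mothers, care staff and those who record in theatre know the arm.
- SSC duration and the first-feed outcomes are assessed open-label.
- Glucose, lactogenesis II and exclusive breastfeeding are called blinded only if the person recording them did not see the allocation; otherwise they are labelled open-label.
- Analysts work with coded groups, as now intended.

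In section 2.8.1, define the primary outcome from the scheduled 1, 3 and 6 hour meter readings, with the time of each recorded, and state that symptom-prompted rechecks neither add nor replace an event. This governs only which readings count in the analysis; it changes nothing in how infants are monitored or treated.

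The cost is protocol wording and a recorded time for each reading. Sample size and care are unchanged, and no extra staff are needed unless the sponsor wishes to claim blinded assessment of the later outcomes and has no one suitable. The downside is that the stated blinding becomes less favourable.

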1 **Immediate Skin-to-Skin Contact and Breastfeeding During Caesarean Section: A**
2 **Randomized Controlled Trial on Early Neonatal Hypoglycemia in Late Preterm**
3 **and Term Infants**

4 **1. Introduction**

5 Neonatal hypoglycemia is a common and serious metabolic issue in late preterm
6 and term infants, potentially leading to severe neurodevelopmental sequelae if not
7 promptly managed¹. The World Health Organization strongly endorses skin-to-skin
8 contact (SSC), recommending that the practice should begin immediately after birth by
9 placing the naked infant on the mother's bare chest. This approach is vital for stabilizing
10 glucose levels and supporting neonatal adaptation to extrauterine life².

11 Despite the well-documented advantages of SSC in vaginal births, such as thermal
12 regulation, breastfeeding initiation, and bonding, implementing this practice during
13 cesarean sections (CS) presents significant challenges³. These challenges primarily
14 stem from the need to maintain a sterile surgical environment and the logistical
15 complexities of performing SSC immediately post-surgery⁴. However, research
16 indicates that immediate, continuous SSC within 5–10 minutes of neonatal delivery
17 during and after CS can foster earlier breastfeeding initiation, increase breastfeeding
18 self-efficacy and exclusive breastfeeding rates during hospitalization, and enhance
19 maternal satisfaction⁵. Additionally, it can reduce the incidence of neonatal
20 hypothermia and cumulative blood loss within 24 hours postpartum.

21 Despite the advantages noted in the literature, there is limited systematic research
22 on the implementation of SSC during CS and its specific impact on neonatal
23 hypoglycemia and breastfeeding outcomes⁴. This study aimed to address this gap by
24 evaluating the effects of immediate SSC and breastfeeding during CS on early neonatal
25 hypoglycemia in late preterm and term infants. Through a randomized controlled trial,
26 we sought to provide robust evidence on the feasibility and benefits of integrating these
27 practices into standard CS protocols. Our findings could inform clinical guidelines,
28 enhance care practices for cesarean deliveries, and ultimately improve neonatal health
29 outcomes and breastfeeding success.

1
2
3
4
5
6
7
8
9
10
11
12
13
14
15
16
17
18
19
20
21
22
23
24
25
26
27
28

2. Material and Methods

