26 remains in SSC with the mother for as long as possible, ideally throughout the cesarean.
27 The obstetric nurse monitors the neonate during SSC and assists the mother in holding
28 the newborn. In cases of maternal or neonatal discomfort, the neonate may be handed

IMMEDIATE SKIN-TO-SKIN CONTACT DURING CAESAREAN SECTION

1 to an obstetric nurse or pediatrician. All neonates are examined by the pediatrician
2 within an hour post-delivery in the recovery ward.

3 2.6.2 Immediate SSC and early breastfeeding initiation

4 Upon birth, the neonate is promptly placed prone on the mother's chest, with their
5 head turned to one side for optimal skin contact. The drying process begins within 5
6 seconds and is completed within 20 to 30 seconds while the neonate remains on the
7 mother's chest. Delayed cord clamping is practiced, with the cord clamped
8 approximately 1-3 minutes after birth. Breastfeeding cues such as tongue movements
9 or head turning are monitored, and the obstetric nurse assists the mother in initiating
10 breastfeeding as soon as possible. SSC continues throughout the cesarean procedure,
11 and upon completion, the newborn is temporarily separated from the mother for safety
12 during transfer to the surgical cart. SSC is resumed immediately post-transfer and
13 continues for a cumulative duration of at least 90 minutes. The neonate's skin color,
14 breathing, and feeding responses are continuously observed.

15 2.6.3 Routine newborn care

16 Newborn eye care, vitamin K1 administration, immunizations, weighing, and
17 standard examinations are conducted before the neonate is transferred to the ward.

18 **2.7 Control Group (CG)**

19 2.7.1 Delayed SSC and breastfeeding

20 The neonate is dried within 20-30 seconds after birth, the cord is clamped after 1-
21 3 minutes, and then the neonate is sent to the ward to wait for the mother to complete
22 the surgery. Immediate SSC is initiated within one hour after birth and maintained with
23 the mother for at least 90 minutes post-surgery, during which the neonate's skin color
24 and breathing are continuously monitored. The obstetric nurse supports the mother in
25 initiating breastfeeding at the earliest opportunity.

26 2.7.2 Routine newborn care

27 Newborn eye care, vitamin K1 administration, immunizations, weighing, and
28 standard examinations are conducted before the neonate is transferred to the ward.

29 **2.8 Outcome Indicators**

IMMEDIATE SKIN-TO-SKIN CONTACT DURING CAESAREAN SECTION

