4 **2.10 Sample Size**

5 The sample size was determined based on a preliminary trial with 258
6 participants⁵. In this trial, the Early Essential Newborn Care (EENC) group exhibited
7 a lower incidence of neonatal hypoglycemia compared to the control group receiving
8 conventional care (0 vs. 5.3%, $P=0.007$). Using G*Power software version 3.1.7, with
9 a two-sided type I error (α) of 0.05, a power ($1 - \beta$) of 90%, test family set to 'exact,'
10 and the statistical test 'proportions: inequality, two independent groups,' it was
11 calculated that at least 148 patients were required in each group. To account for an
12 anticipated 20% dropout rate, the total sample size was adjusted to 356 participants,
13 with 178 allocated to each group.

14 **2.11 Statistical Analysis**

15 The data analysis will be performed using SPSS 21.0 (SPSS Inc., Chicago, IL).
16 Quantitative variables will be expressed as mean \pm standard deviation. The T-test will
17 be employed for normally distributed data, while the Mann-Whitney U test will be
18 used for non-normally distributed data. Categorical variables will be summarized as
19 frequencies and percentages and analyzed with the Chi-squared test. All statistical
20 tests are two-sided, and a P-value of less than 0.05 is considered significant.

21 **2.12 Ethics**

22 This study will adhere to the ethical standards set by the relevant institutional and
23 national review committees. Approval was granted by the Institutional Research
24 Human or Animal Ethics Committee of Qingdao Municipal Hospital (2023 Lin Shen
25 Zi No. 122), and all procedures complied with the revised 2013 Declaration of
26 Helsinki.

IMMEDIATE SKIN-TO-SKIN CONTACT DURING CAESAREAN SECTION

References

- 1
- 2 1. Roeper M, Hoermann H, Kummer S, Meissner T. Neonatal hypoglycemia: lack of
3 evidence for a safe management. *Front Endocrinol (Lausanne)*. 2023;14:1179102.
- 4 2. World Health Organization W. Skin-to-skin contact helps newborns breastfeed.
5 [https://www.who.int/westernpacific/news-room/feature-stories/item/skin-to-skin-
7 contact-helps-newborns-breastfeed](https://www.who.int/westernpacific/news-room/feature-stories/item/skin-to-skin-
6 contact-helps-newborns-breastfeed). Accessed July 23, 2024.
- 8 3. Immediate and Sustained Skin-to-Skin Contact for Healthy Late Preterm and Term
9 Newborns After Birth: AWHONN Practice Brief Number 14. *Journal of Obstetric,
10 Gynecologic & Neonatal Nursing*. 2021;50(6):e13-e15.

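### Section 2.7.1 labels the control's skin-to-skin contact both delayed and immediate, and section 2.10 borrows its 5.3% control rate from conventional care without showing that it fits this early-contact control

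*Protocol*

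**What the plan says.** Section 1 states the aim as "evaluating the effects of immediate SSC and breastfeeding during CS on early neonatal" hypoglycemia. It names no comparator. The same section describes immediate, continuous SSC in earlier research as beginning 5 to 10 minutes after delivery.

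Section 2.6.2, on the experimental arm, has Immediate SSC in its heading and begins: "Upon birth, the neonate is promptly placed prone on the mother's chest, with their" head to one side. SSC runs through the operation, pauses for transfer, and resumes to a cumulative minimum of 90 minutes. The nurse helps start breastfeeding as soon as possible.

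Section 2.7.1, on the control arm, is headed "2.7.1 Delayed SSC and breastfeeding". The infant is dried, the cord is clamped, and the infant goes to the ward until the mother's operation is over. The text then reads "the surgery. Immediate SSC is initiated within one hour after birth and maintained with" "the mother for at least 90 minutes post-surgery, during which the neonate's skin color" and breathing are watched. The nurse supports the mother in "initiating breastfeeding at the earliest opportunity".

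Section 2.8.1 has blood glucose "assessed using the Stat Strip Xpress glucose meter at 1, 3, and 6 hours after birth".

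Section 2.10 takes the planning rates from an earlier trial of 258 participants, in which the early essential newborn care group had "a lower incidence of neonatal hypoglycemia compared to the control group receiving" conventional care, 0 vs 5.3%. From these it derives 148 per group at two-sided 5% and 90% power with an exact test.

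**The concern.** There are two linked problems.

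First, one term names both arms. Under its heading the control has delayed SSC; under its body text it has immediate SSC, which is what the experimental arm and the trial title are called. The surrounding sentences let a reader work out the intended contrast, but the label does not, and the objective does not say what immediate SSC is compared with.

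Second, the planned effect rests on a control described in other terms. This trial's controls receive SSC within an hour of birth, for at least 90 minutes, with help to breastfeed. If that care itself prevents some hypoglycemia, the control rate could be below 5.3%, and the stated 90% power would belong to a larger contrast than the one being run. A result showing no difference would then need careful wording: it would concern starting during rather than after surgery, at uncertain power.

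**Working it through.** **The two arms side by side (sections 2.6 and 2.7)**

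| Element | Experimental | Control |
|---|---|---|
| Drying | completed by 20-30 s, on the mother's chest | within 20-30 s |
| Cord clamping | about 1-3 min | 1-3 min |
| SSC start | at birth, during surgery | after surgery, within 1 h of birth |
| Minimum SSC | 90 min, cumulative | 90 min |
| Breastfeeding support | as early as possible, during surgery | as early as possible, once reunited |
| During surgery | with the mother | separated, in the ward |

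A control infant who starts at the latest permitted time and is held continuously reaches the minimum at 60 + 90 = 150 min, before the 3 h (180 min) reading. Both arms can therefore have met the same minimum by the 3 h and 6 h readings. At the 1 h reading the control may have had little or no SSC.

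**The plan's own figure**

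Inputs from section 2.10: rates 0 and 5.3%, two-sided alpha 0.05, power 90%, exact test, 148 per group. Full binomial enumeration of two-sided Fisher's test gives 80.2% power at 148 per group, and 173 per group are needed for 90%. So 148 does not reproduce as stated. That is a separate error, but it sets the baseline against which any effect of the comparator must be read.

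**Power as the control rate falls**

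With a true rate of 0% in the experimental arm, that arm has no events. Power is then the chance that the control arm has enough events, X ~ Binomial(148, p), to reach significance.

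- Two-sided Fisher, 0 vs c events: c = 5 gives P = 0.060 and c = 6 gives P = 0.030. Six events are needed, so power = P(X ≥ 6).
- Uncorrected chi-squared, 0 vs c events: the statistic is c / (1 − c/296). c = 3 gives 3.03 and c = 4 gives 4.05, against the critical value 3.84. Four events are needed, so power = P(X ≥ 4).

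| Control rate p | Expected events, 148p | Fisher, P(X ≥ 6) | Chi-squared, P(X ≥ 4) |
|---|---|---|---|
| 5.3% (section 2.10) | 7.8 | 80% | 96% |
| 4.0% (assumed) | 5.9 | 54% | 85% |
| 3.0% (assumed) | 4.4 | 29% | 65% |
| 2.65% (assumed, half of 5.3%) | 3.9 | 20% | 55% |

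Both columns are relevant: section 2.10 sizes the trial on an exact test, while section 2.11 plans a chi-squared test. The part of the loss due to the comparator is the fall within a column from its 5.3% row, for example 80% to 54% or 96% to 85% at a control rate of 4.0%. It is not the fall from 90%.

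**The case against.** The strongest defence is that the contrast is close to the declared question. The title and aim concern SSC and breastfeeding during cesarean section, and starting during versus after the operation addresses that. The design is called pragmatic and the hospital is accredited as baby-friendly, so a control with early postoperative SSC is a reasonable choice. This stands: the control arm is not a design fault, and the objective only needs to name it.

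A reader might infer that the arms hardly differ, being the same care moved by an hour with the same dose by 3 h. The text does not support this. The 90 minutes is a minimum in both arms, and intraoperative SSC is to last as long as possible, so equal minimums do not show equal exposure. The arms also differ in separation during surgery and in intraoperative breastfeeding. Nor is the control start unbounded on the early side: it cannot precede the end of the operation, although no clock time is set.

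A reader might also infer that the source trial's control had no early SSC and that true power is therefore 20% or 29%. The protocol does not say what conventional care comprised. It shows a different description, not a proven difference, and it gives no rate for a control with SSC within the hour. On the planned chi-squared test, power is still 85% at a control rate of 4.0% with 148 per arm; it falls well below 80% only if the rate is about 3% or less, which nothing in the document establishes.

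Part of the remedy is already in place: section 2.9 collects SSC duration and first-breastfeeding initiation, the latter timed to the minute under section 2.8.2. SSC start time is not listed.

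**Conclusion.** The point holds as a contradiction in the arm definition and an unsupported carry-over in the sample-size basis. The heading and body of section 2.7.1 use opposite labels, and the body's label is the experimental intervention's. The 90% in section 2.10 is stated without qualification although it depends on a 5.3% rate from a control described only as conventional care.

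The size of the consequence is conditional. If the control rate here is 2.65% to 4.0% and the experimental rate is 0%, power at 148 per arm is 20% to 54% by Fisher or 55% to 85% by uncorrected chi-squared. Those control rates are assumptions chosen to show sensitivity, and the actual loss cannot be estimated from the document. Under either test, each assumed rate leaves power below the stated 90%.

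**What to change.** 1. Reconcile the heading and body of section 2.7.1 so that one term describes the control's SSC and a different one the experimental arm's. The choice of term is the sponsor's.
2. In the objective, name the comparator: SSC and breastfeeding started during surgery versus started after surgery within one hour of birth. Limit the conclusion to that contrast.
3. In section 2.9, add SSC start time in both arms beside the duration already collected, and report the separation achieved.
4. In section 2.10, say that 5.3% comes from a conventional-care control, justify its use for this control or say that it is assumed, and replace the single 90% with power over a control range such as 2.65% to 5.3%, naming the test used. The failure of 148 to reproduce should be corrected in its own right.

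The cost is protocol wording and one time field, with no more patients and no change in care. The downside is a less favourable stated power and a narrower claim.

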2.1 Study Design

This study will adopt a pragmatic, parallel-design, two-arm randomized controlled exploratory framework. The article’s reporting will adhere to the Consolidated Standards of Reporting Trials (CONSORT) guidelines⁶.

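### Onset of lactogenesis II can be right-censored at discharge, but section 2.11 gives only mean ± SD with a t-test or Mann-Whitney test and no rule for women without onset

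*Protocol*

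**What the plan says.** Protocol section 2.8.2 (B) introduces the outcome as "Onset of lactogenesis II, approximately 72 hours post-delivery". It is assessed from "delivery to pre-discharge, with timing recorded to the hour postpartum". The protocol states no minimum stay, no common hour to which all women are observed and no contact after discharge.

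Protocol section 2.11 gives one general rule: "Quantitative variables will be expressed as mean" with standard deviation. The t-test is for normally distributed data, and the Mann-Whitney U test is to be "used for non-normally distributed data". Categorical variables get a chi-squared test. Section 2.11 does not assign a test to each outcome, names no time-to-event method, and gives no value or rank to a woman without onset by discharge. It does not say that such women are dropped either.

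Section 2.1 describes the trial as a "two-arm randomized controlled exploratory framework".

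**The concern.** The outcome is a time to event whose observation ends at each woman's discharge. Its expected time, about 72 h, is not separated from the end of observation by any stated margin. For a woman still without onset, all that is known is that onset comes later than her discharge hour.

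A mean, an SD and a t-test need a number for every woman, and she has none. Choosing between t-test and Mann-Whitney by normality does not solve this, because a Mann-Whitney test can keep her only if someone decides how she is ranked. Without a rule, the likely default is to analyse only the women with a recorded time. That removes the latest onsets. If the intervention brings onset forward, more are removed from the control arm than from the experimental arm, and the observed difference moves toward zero. A choice between dropping, imputing and ranking would also be left until the data are known.

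**Working it through.** The protocol states no figure for this outcome that could be reproduced, so the calculation below only illustrates the possible size.

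**Inputs from the protocol.** Onset at about 72 h and observation to discharge (2.8.2 (B)); two-sided 0.05 (2.11); 148 evaluable women per arm (2.10).

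**Assumptions not in the protocol.** Normally distributed onset; control mean 72 h, which is one reading of the stated 72 hours; SD 12, 18 or 24 h; true gain 8 h, so experimental mean 64 h (a gain of 4 h was also tried with SD 12 h); one common discharge hour D of 72, 84, 96 or 120 h.

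**Step 1: share without onset.** With a = (D − μ)/SD, the share is 1 − Φ(a).

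**Step 2: mean among women with an observed time.** This is the truncated-normal mean, μ − SD·φ(a)/Φ(a).

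Worked case, SD 18 h and D = 84 h:
- Control: a = 12/18 = 0.667; share without onset 1 − 0.748 = 25%; mean 72 − 18 × 0.3194/0.7475 = 72 − 7.69 = 64.31 h.
- Experimental: a = 20/18 = 1.111; share 1 − 0.867 = 13%; mean 64 − 18 × 0.2152/0.8667 = 64 − 4.47 = 59.53 h.
- Observed difference: 64.31 − 59.53 = 4.78 h, against a true 8 h.

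**Step 3: power.** 3,000 simulated trials per setting, 148 per arm, times rounded to the hour.

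In the table, each cell gives the values for SD 12 / 18 / 24 h, with a true gain of 8 h.

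| Discharge | Without onset, control vs experimental | Observed difference if left out (h) | Mann-Whitney power, observed times only | Mann-Whitney power, late women ranked last |
|---|---|---|---|---|
| 72 h | 50% vs 25% / 50% vs 33% / 50% vs 37% | 3.55 / 3.32 / 3.21 | 83 / 44 / 26% | 100 / 94 / 73% |
| 84 h | 16% vs 5% / 25% vs 13% / 31% vs 20% | 5.80 / 4.78 / 4.26 | 99 / 74 / 42% | 100 / 96 / 78% |
| 96 h | 2.3% vs 0.4% / 9% vs 4% / 16% vs 9% | 7.47 / 6.29 / 5.43 | 100 / 89 / 58% | 100 / 96 / 81% |
| 120 h | 0% vs 0% / 0.4% vs 0.1% / 2.3% vs 1.0% | 8.00 / 7.85 / 7.31 | 100 / 96 / 76% | 100 / 96 / 80% |

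Log-rank power, censored at discharge, is 100% at SD 12 h, 92–94% at SD 18 h and 69–75% at SD 24 h.

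With SD 12 h and a gain of 4 h, Mann-Whitney power on observed times versus ranked last is 26% vs 74% at 72 h, 59% vs 79% at 84 h, 75% vs 79% at 96 h and 79% vs 79% at 120 h.

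**Step 4: no true effect, equal discharge timing.** Rejection rates were 4.5–5.9% for every test and setting, which is nominal.

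**The case against.** The strongest reply is that section 2.11 is a generic paragraph and that handling of unobserved values is often left to a statistical analysis plan, which may exist. Section 2.11 also names the Mann-Whitney test, which works well here once late women are ranked last, so only one sentence is missing. Further, nothing in the protocol shows that censoring will be frequent. The 72 hours may be a typical time, an upper expectation or part of the definition, and length of stay is not given. Attenuation arises only if women without onset are left out, which the protocol does not say.

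Much of this stands, and it limits the size of the point. The amount of censoring cannot be derived from the protocol, and if all women stay well beyond 96 h the problem nearly vanishes. No false-positive risk is shown under equal discharge timing. A false difference would need discharge timing to differ between the arms, which the protocol does not state.

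What does not stand is that this is only missing detail. Section 2.11 fixes mean ± SD as the summary for quantitative variables, with a t-test as one of its two branches, and neither can use a woman with no observed time. A later plan that added a ranking rule would still have to depart from the stated summary for this outcome.

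**Conclusion.** The concern holds, as a minor one. The method stated in 2.11 does not fit an outcome that can be right-censored at discharge. If women without onset are left out, the loss under the assumptions above runs from more than half of the true difference (8 h observed as 3.2 to 3.6 h at a 72 h discharge) to nothing (SD 12 h, 120 h). Mann-Whitney power at SD 18 h falls from 94% to 44% at 72 h and does not fall at 120 h. These figures rest on an assumed mean, SD, gain and discharge hour. The direction, toward no difference when the intervention works, does not depend on the exact values within the range tried. One secondary outcome of an exploratory trial is affected; the primary outcome and the sample size are not.

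**What to change.** In 2.11, state that onset of lactogenesis II is analysed as a time to event censored at discharge, with Kaplan-Meier medians and a log-rank test. If all women are observed to one common hour, use instead a Mann-Whitney test with women without onset ranked last; this had the same power as log-rank or more in every setting computed. In either case report the number without onset by discharge in each arm. The discharge hour must be available. It is not among the items listed in 2.9, so take it from hospital records if it is not already collected.

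The cost is one or two sentences, with no extra patients or visits. Where almost nobody is censored, log-rank gives up a little power to the t-test on observed times:
- 8 h gain, 120 h: 94% vs 97% (SD 18 h) and 73% vs 78% (SD 24 h).
- 4 h gain, SD 12 h: 74% vs 77% at 96 h and 74% vs 81% at 120 h.

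Mann-Whitney with late women ranked last stays within about 2 points of the t-test there. Log-rank also assumes that discharge does not depend on whether milk has come in, which the protocol does not settle and which the revised text should address.
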